Lowering and maintaining sUA concentrations below the level of 'supersaturation' is absolutely essential in reducing the total body urate burden and achieving long-term benefits. Targeting a slightly lower threshold of < 6.0 mg/dl accounts for both the issues of day-to-day variability in sUA and assay imprecision (estimated in College of American Pathologists Proficiency Testing [CAP PT] to approach 4 to 5%). Although the predominance of literature suggests no significant diurnal variation in sUA (73, 74), others have suggested a small degree of such variability approaching 0.5 mg/dl (75). In particular, this level of sUA is considered an evidence-based target for treatment, and necessary to achieve outcomes pertinent to patients, such as reduction of flare frequency (7, 76). Understanding its essential role in gout treatment, we have adopted the biochemical threshold of a sUA concentration below 6.0 mg/dL as a secondary end-point, and one which regulatory agencies require for approval (11, 13).

To facilitate point-of-care ULT dose titration, all sUA measurements will be performed by the clinical laboratory at the participating study site. Importantly, sUA measurement is internationally standardized and readily accessible across all participating clinical laboratories. The prevailing technique used for sUA measurement used in the U.S. (including VA centers and RAIN sites) uses the Trinder reaction with uricase, an assay that has been shown to be highly reliable with between-laboratory and between-method coefficients of variation routinely below 5% (77).

- 3) Determining if gout flares in Phase 3 differ in those who reach a target sUA of < 6.0 mg/dl compared with those who do not by 48 weeks.

As detailed above, achieving a sUA goal of <6.0 mg/dl is a universally recommended treatment goal for ULT in practice as well as regulatory trials. However, the true relationship of achieving this target with reducing gout flares has not been well documented in long-term clinical trials. The design of this trial will allow us to address this important question. Specifically, we will compare the gout flare rates in Phase 3 of those who did and did not achieve a sUA of < 6.0 mg/dl at the end of Phase 2.

- 4) The impact of study treatments and sUA levels on health-related quality of life.

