tophus found at the time of the baseline evaluation on the hands, elbows, feet, or ears (i.e., the most common sites for tophi). In addition to having face validity, the tape measurement technique is inexpensive, requires minimal training, and a very short time for acquisition (estimated to be < 5 minutes). Moreover, this technique yields excellent inter- and intra-observer reliability with interclass correlation coefficients exceeding 0.9. In a 52-week study, patients with tophaceous gout achieving a final serum urate < 6.0 mg/dl demonstrated a 75% reduction in tophus size using this technique (11).

6) The impact of treatment on the flare rate over time (comparison of flare rates during each phase).

To determine whether the total number of gout flares differs between the two treatment groups the total flare numbers occurring during observation (week 0 to 72) will be compared. Recognizing that the duration of a gout flare typically extends from several days to 2-3 weeks, and that it may sometimes be difficult for patients to distinguish between two or more back-to-back flares and one persistent but fluctuating flare, a maximum of one gout flare will be counted for each one-month observation period. Thus, as an example during Phase 3 (24 weeks) patients could experience a number of gout flares ranging from 0 to 6 flares.

7) Exploring the tolerability/toxicity of the two ULT.

Toxicity data will be carefully collected throughout the 72 weeks of the trial (See Section XI, Baseline and Follow-up Assessment) and compared across treatment arms. Adverse events will be summarized using Medical Dictionary for Regulatory Activities (MedDRA) terminology and reported by count and frequency (%) for participants reporting an event for each term. Toxicity data that will be systematically collected include rises in sUA levels, serum creatinine, CBC, liver function tests (LFTs), blood pressure and reports of skin rashes. The frequency of cardiovascular safety events of interest will also be collected and analyzed, with particular emphasis on cardiovascular and all-cause mortality. Investigators will report other treatment-related adverse events should they encounter them. All hospitalizations and other adverse events defined as serious per ICH guidelines will be collected and analyzed by treatment group.

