Toxicity events include rises in sUA levels, adverse changes in serum creatinine, CBC, liver function tests (LFTs), blood pressure, and the incidence of skin rashes. The incidence of cardiovascular events of interest, with particular emphasis on cardiovascular and all-cause mortality, will also be included in this analysis. Within each Phase we will determine if the incidence of such events differs between treatments. In the Phase 3 analysis baseline covariates will include the summary of toxicity events during Phases 1 and 2 as well as the 48-week sUA level. As in the sixth secondary analysis the same statistical methods for Poisson counts will be used to express time-dependent events.

At each clinic visit we will assess the count of each type of major side effect episodes between visits. Deviations from the titration protocol will be modeled as a binary factor. We will model counts that have substantial variation as Poisson random variables. These outcome measures include each count and the aggregate count. These counts will be coarsened into binary outcomes of no events versus one or more events. The analyses will compare treatments using a longitudinal repeated measures analysis with Poisson count, negative binomial counts, and binary outcomes (PROC GLIMMIX and GENMOD in SAS). Missing data methods will address potential censoring of events among patients who fail to attend clinic visits. We will run this same analysis using the biological threshold of sUA <6.8 mg/dl after 48 weeks.

- 8) To describe the effects of baseline covariates and time-dependent covariates on the primary results.

Baseline data include demographic characteristics (e.g. age, sex), disease history including CKD level, presence of tophi at baseline, height, weight, laboratory values, medications, other comorbidities, and quality-of-life measures. Data obtained often after baseline include sUA values, titration levels, side effects, and gout flare counts. Many baseline measurements are repeated at 24 and 48 weeks. All data obtained before Phase 3 may be used as baseline factors for Phase 3 analyses such as the primary hypothesis and secondary object #1. Secondary analyses 2-7 can adjust for covariates obtained at baseline and at 24 weeks.

All major analyses will be repeated on the per-protocol population with adherence and non-adherence as defined above. The objective is to either confirm our results or detect that adherence to treatment alters the result.

Missing Data

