Toxicity data will be carefully collected throughout the 72 weeks of the study and compared across treatment arms. Toxicity data include rises in sUA levels, serum creatinine, CBC, liver function tests (LFTs), blood pressure, cardiovascular safety events of interest, hospitalization,

and reports of skin rashes.

8) The effects of baseline covariates and time-dependent covariates on the primary results.

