  - a. We will model the number of gout flares, which can have substantial variation, as Poisson random variables. We will use Poisson regression to compare treatments using a longitudinal repeated measure (PROC GLIMMIX and GENMOD in SAS). Missing data methods will address potential censoring of events among patients who appear to fail to report flares.
  - b. Flare counts will be analyzed separately during Phases 1, 2, and 3 because dose titration during Phase 1 tends to increase the counts, and this effect may still persist in Phase 2, particularly for those still undergoing dose titration; participants are expected to be in steady-state by Phase 3.
  - c. Phase 2 analysis will consider prophylactic treatment after a gout flare and severe side effects of treatment as predictors of subsequent counts.
  - d. During Phase 3 the same set of factors as well as Phase 2 counts will be used to predict gout flare counts. These time-dependent associations will require a mixed effects model using an auto correlated AR(1) variance-covariance to model the series of events.
  - e. For these analyses we may treat the counts as continuous measures in order to introduce more subtle variance-covariance structure and a variety of random effects.
- 7) To determine the patterns of tolerability/toxicity for each treatment during Phase 3 and then overall from weeks 1-72.
  - a. Toxicity events include rises in sUA levels, adverse changes in serum creatinine, CBC, liver function tests (LFTs), blood pressure, and the incidence of skin rashes. The incidence of cardiovascular events of interest will also be included in this analysis.
  - b. Within each Phase we will determine if the incidence of such events differs between treatments. In the Phase 3 analysis baseline covariates will include the summary of toxicity events during Phases 1 and 2 as well as the week 48 sUA level. As in the sixth secondary analysis the same statistical methods for Poisson counts will be used.
  - c. At each clinic visit we will assess the count of each type of major side effect episodes between visits. The analyses will compare treatments using a longitudinal repeated measures analysis with Poisson count, negative binomial counts, and binary outcomes

(PROC GLIMMAX and GENMOD in SAS). Missing data methods will address potential censoring of events among patients who fail to attend clinic visits.

- 8) To describe the effects of baseline covariates and time-dependent covariates on the primary results.

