**Table C6. Study Secondary Outcome Events – Part V**

Phase	Toxicity Events	Sample (n=)	Form Location
Rise in sUA levels			
1	Mean ± SD	N (%)	Clinical Biochem Lab
2	Mean ± SD	N (%)	Clinical Biochem Lab
3	Mean ± SD	N (%)	Clinical Biochem Lab
Overall	Mean ± SD	N (%)	Clinical Biochem Lab
Skin Rashes			
1	0	N (%)	Rash Adverse Event
	1-2	N (%)	
	3+	N (%)	
2	0	N (%)	Rash Adverse Event
	1-2	N (%)	
	3+	N (%)	
3	0	N (%)	Rash Adverse Event
	1-2	N (%)	
	3+	N (%)	
Overall	0	N (%)	Rash Adverse Event
	1-2	N (%)	
	3+	N (%)	

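### Serum urate rises of unstated size are classed as toxicity events although serum urate is an efficacy measure, so the toxicity summaries mix poor urate control and noise with harm

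*Protocol*

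**What the plan says.** Rises in sUA are classed as toxicity in four places, each time without a size, a reference value or a confirmation rule:

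- Protocol VII, secondary end point 7: "Toxicity data that will be systematically collected include rises in sUA levels, serum creatinine, CBC".
- Protocol VIII, secondary objective 7: "Toxicity events include rises in sUA levels, adverse changes in serum creatinine, CBC".
- SAP 3.5.2, item 7: "Toxicity data include rises in sUA levels, serum creatinine, CBC, liver function tests (LFTs), blood pressure".
- SAP 5.5, objective 7: "Toxicity events include rises in sUA levels".

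Both analysis sections compare the incidence of such events between treatments within each phase. Both also use a summary of Phase 1 and 2 toxicity events as a Phase 3 covariate, beside the week 48 sUA.

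The Protocol adds that the outcome measures include each separate count and an aggregate, and then: "These counts will be coarsened into binary outcomes of no events versus one or more events". SAP 5.5 names binary outcomes but neither the aggregate nor this reduction. SAP Table C6 gives "Rise in sUA levels" its own block by phase, apart from skin rashes, with no aggregate row.

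Elsewhere sUA measures efficacy. The proportion reaching sUA below 6.0 mg/dl is secondary outcome 2, and Protocol VIII calls a mean of 6.0 or more over weeks 36, 42 and 48 a treatment failure.

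**The concern.** A higher urate value during treatment most naturally means too little drug effect, missed doses or measurement variation. The Protocol says as much: section X allows up-titration to be deferred when an increase is thought to come from laboratory error or non-adherence. None of these is a harm of the drug.

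Two consequences follow. The first is directional. If one arm has poorer urate control or adherence, it shows more rises, and the plan reports them as more toxicity. Blinding does not prevent this. The second is dilution. With no minimum size, ordinary variation produces events in both arms at similar rates and pulls any pooled contrast towards no difference. An open definition also leaves the threshold to be chosen after the data are seen.

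The Protocol's provider and patient surveys (section III) ranked tolerability second and sUA reduction third, as separate priorities. This event list merges them.

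**Working it through.** The documents give no event rate, threshold or power for the toxicity comparison, so there is no figure of theirs to reproduce. The check asks how often a participant with a constant true sUA would show a rise between consecutive draws.

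**Inputs from the documents.** Protocol Table 5 schedules sUA at weeks 24, 30, 36, 42, 48, 60 and 72, which is seven draws. Dose escalation ends before week 36, which leaves five draws (36, 42, 48, 60, 72) on a settled dose. Protocol VII, end point 2, puts assay imprecision at about 4 to 5%.

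**Assumed single-draw SDs (mg/dl).**
- 0.20 is 4% of 5.0.
- 0.27 is 4.5% of 6.0.
- 0.275 is 5% of 5.5.
- 0.37 adds an assumed biological SD of 0.25: √(0.275² + 0.25²) = 0.37.
- 0.35 and 0.5 serve only to show the range.

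**Any rise counts.** For k exchangeable draws, only a strictly falling order shows no rise, so P(at least one rise) = 1 − 1/k!, whatever the SD.
- k = 7: 1 − 1/5040 = 99.98%
- k = 5: 1 − 1/120 = 99.2%
- k = 4 (clinic visits only, weeks 36, 48, 60, 72): 1 − 1/24 = 95.8%
- k = 3 (weeks 48, 60, 72): 1 − 1/6 = 83.3%

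Ties from rounded results lower these somewhat. The expected number of rises is (k − 1)/2, or 2.0 per participant for k = 5.

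**A minimum size is set** (simulation, normal noise, participants with at least one rise):

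| Rise of about | 5 draws, SD 0.20 to 0.37 | 7 draws, SD 0.20 to 0.5 |
|---|---|---|
| 0.5 mg/dl | 15 to 58% | 22 to 88% |
| 1.0 mg/dl | 0.1 to 11% | 0.1 to 41% |
| 2.0 mg/dl | 0.03% or less | not needed |

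Within the seven-draw column, rises of 0.5 or more occur in 48% at SD 0.27 and 70% at SD 0.35.

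**Effect on the none-versus-any outcome.** Suppose true harm affects 20% and 30% of the two arms (an assumption) and noise rises occur independently with probability q in both. The difference becomes (30 − 20) × (1 − q) points.
- q = 0.48: 10 × 0.52 = 5.2 points
- q = 0.99: 10 × 0.01 = 0.1 point

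**Effect on the aggregate count.** Let h be true harm events per participant, with a true rate ratio of 1.5 (both assumed), and u the noise rises per participant. The observed ratio is (u + 1.5h)/(u + h), for h from 0.2 to 1.0 and five draws.
- Any rise, u = 2.0: (2.0 + 0.3)/2.2 = 1.05 to (2.0 + 1.5)/3.0 = 1.17
- Above 0.5 mg/dl, u = 0.15 to 0.68: 1.11 to 1.43
- Above 1.0 mg/dl, u = 0.001 to 0.11: 1.32 to 1.50
- Above 2.0 mg/dl: about 1.50

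The directional effect cannot be sized. It needs a difference in urate control between arms, and Protocol VIII expects roughly equal numbers to reach the target in each arm.

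**The case against.** The best reply is that these counts carry little of the safety evaluation. Each toxicity type is analysed on its own. Adverse events by MedDRA term, serious adverse events, hospitalizations, cardiovascular events, deaths and rash are compared outside any aggregate, and tolerability in stage 3 CKD uses adverse events, serious adverse events and related withdrawal. Every secondary analysis is labelled exploratory. All of this stands, and it limits the importance of the point.

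Entry into the aggregate is also an inference. The Protocol's counts are of major side effects between visits, and it does not say whether an sUA rise is one; the SAP names no aggregate. The inference is the natural one, because the same paragraphs open by defining toxicity events and offer no other list. The by-phase incidence comparison and the Phase 3 covariate do not depend on it.

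A reader might go further and infer that noise dominates the whole tolerability comparison. The documents do not support that. It would need a very low threshold, harm rates that they do not give, and the absence of the separate comparisons above. Nor do they support treating 0.5 mg/dl as a day-to-day SD. Protocol VII reports it as diurnal variation suggested by some sources, against a literature that mostly finds none, so the 88% figure is only an upper illustration. Noise that is equal in both arms dilutes a contrast; it does not favour a drug.

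Finally, the other laboratory items in the list also lack a size. On an any-rise rule, five creatinine values would give the same 99.2%. Removing sUA does not cure that, but those items are at least plausible harms, and the analysis sections restrict creatinine to adverse changes. An sUA rise is in the wrong category whatever its size.

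**Conclusion.** The point holds in a limited form. Both documents class sUA rises of unstated size as toxicity although sUA is an efficacy measure. As written, the rises enter the by-phase incidence comparison and the Phase 1-2 toxicity summary used in the Phase 3 model, where urate then appears twice, once under a toxicity label. They probably also enter the Protocol's aggregate and none-versus-any counts.

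If any rise counts, 99% or more of participants with a stable level have an event over five to seven draws, and the none-versus-any outcome is close to uninformative. With a threshold near 1.0 mg/dl the share falls to 0.1 to 11% over five draws at SDs up to 0.37, and near 2.0 mg/dl it is negligible. These figures rest on a constant true level, normal independent noise and the assumed SDs. The dilution examples also rest on assumed harm rates.

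The misclassification does not depend on those assumptions: a between-arm difference in urate control or adherence would be reported as a difference in toxicity. The harm is confined to the toxicity summaries under objective 7 and does not extend to the trial's safety conclusions as a whole. A correction is worth making because it costs almost nothing.

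**What to change.** 1. Remove sUA rises from the toxicity lists in Protocol VII (end point 7) and VIII (objective 7), in SAP 3.5.2 (item 7) and 5.5 (objective 7), and from the toxicity block of SAP Table C6.
2. State in both documents that sUA rises do not enter the Phase 1-2 toxicity summary covariate or any aggregate or none-versus-any count.
3. Report sUA change by arm as an efficacy or pharmacodynamic result through week 72. Objective 2 is evaluated at the end of Phase 2, so its reporting must be extended to weeks 60 and 72; otherwise the Phase 3 urate results now placed in Table C6 would be lost.
4. State in the SAP whether the Protocol's aggregate toxicity count and its reduction to none versus one or more are kept.

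The cost is minor rewording in both documents and one added descriptive sUA table. No new data are needed and the primary analysis is untouched.

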The test of the primary hypothesis compares the treatments without adjustment for any covariates. The secondary analyses, particularly secondary analysis will confirm or not confirm the primary hypothesis by considering variations on the primary analysis including logistic regression models that adjust for covariates. We note that logistic regression analysis yields a treatment odds ratio rather than the difference between proportions. In this case, to carry out the non-inferiority test, we will estimate the difference between treatments by linking the odds ratio to the overall proportion of participants who have one or more gout flares.

In addition to testing the primary hypothesis, extensive descriptive analyses outlined in (BRDP) will compare treatments with respect to selected variables among the demographic, medical history, laboratory values, anthropomorphic, vital sign, quality-of-life, alternative outcome, and side effect variables. Simple unadjusted comparisons will apply Student's t-test to continuous variables, the Wilcoxon test to highly skewed continuous or ordinal variables and will apply the Chi-square test (or Fisher's exact test) to categorical variables.

Non-adherence

Of relevance to this study, observational studies have indicated relatively poor adherence in patients with gout (40, 87-90) However, Dalbeth et al. (91) found that higher doses of allopurinol were associated with sUA levels at target independent of adherence with treatment. Because all study participants will receive active therapies of proven efficacy for lowering sUA levels as well as prophylactic treatment of acute gout symptoms, compliance issues are expected to be minimal in this trial. Other studies in rheumatoid arthritis have shown that if patients are doing well, issues of poor treatment adherence are minimized (92).

Participant adherence to protocol-directed study treatment will be assessed via pill counts, prescription renewals, and participant interview. We will use the question and pill count data to determine if a participant took 80% or more of treatment medication. The per-protocol population will be defined as participants remaining on the same treatment throughout the entirety of the study with 80% adherence.

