The primary analysis follows the ITT principle that adjusts for, at most, a few covariates and seldom directly accounts for non-adherence. We will compare the primary results with the analogous results for the per-protocol participants. Also, we will model the effects of non-adherence in the secondary analyses.

In this case adherence is a time-dependent covariate requiring that the treatment comparison be made using a GEE analysis to account for varying periods of follow-up between treatments.

Secondary Data Analysis

All secondary analyses are descriptive exploratory analyses and will be done with and without covariate adjustment (age, sex, disease severity, comorbidities, etc.). All secondary analyses deal with dropping out in the same way described in the primary analyses

We describe the proposed analysis for each of the eight secondary objectives:

- 1) To compare the efficacy and tolerability of allopurinol and febuxostat in hyperuricemic participants with gout and stage 3 chronic kidney disease (CKD 3) in reducing gout flares.

Based on VISN 1 data, over half the participants should have stage 3 CKD. We will carry out exactly the same non-inferiority analysis proposed for the primary objective but restricted to participants with stage 3 CKD, using only gout flares observed during Phase 3. In addition we will carry out logistic regression analyses that adjust for covariates as described in the confirmatory analyses in objective 8. Also, using the full cohort we will compare gout flare rates of participants with stage 3 CKD to participants with an eGFR ≥ 60 mL/min/1.73m² within a logistic regression model. Tolerability of the two treatments will also be compared in this patient subset and will include comparisons of adverse events, serious adverse events, and related study withdrawal.

- 2) To explore the efficacy of the two ULT dosing regimens in achieving the goal of sUA <6.0 mg/dl evaluated at the end of phase 2. Besides treatment, the primary predictors include the series of sUA measures and dose titrations prior to 48 weeks. This longitudinal analysis will model deviations from the titration protocol.

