## 5.5. Secondary Analysis

All secondary analyses are descriptive exploratory analyses and will be done with and without covariate adjustment (age, sex, disease severity, comorbidities, etc.). In some secondary analyses, we will impute values to explicitly explore the effect of missing data.

We describe the proposed analysis for each of the eight secondary objectives:

- 1) To compare the efficacy and tolerability of allopurinol and febuxostat in hyperuricemic participants with gout and stage 3 chronic kidney disease (CKD 3) in reducing gout flares.
  - a. We will carry out the analogues non-inferiority analysis proposed for the primary objective but restricted to participants with stage 3 CKD, using only gout flares observed during Phase 3. Using the full cohort, we will compare gout flare rates of participants with stage 3 CKD to participants with an eGFR  $\geq 60$  mL/min/1.73m^2 with a logistic regression model.
  - b. Tolerability of the two treatments will also be compared in this patient subset and will include comparisons of proportions of adverse events, serious adverse events, and related study withdrawal during the whole study using logistic regression.
  
- 2) To explore the efficacy of the two ULT dosing regimens in achieving the goal of sUA < 6.0 mg/dl evaluated at the end of phase 2. Besides treatment, the primary predictors include the series of sUA measures and dose titrations prior to 48 weeks. This longitudinal analysis will model deviations from the titration protocol.
  - a. The analysis for these longitudinal data will be the mixed effects model with a variance-covariance structure that assumes auto correlated AR(1) sUA measurements over time. We will use PROC MIXED in SAS. At each clinical visit a binary factor will indicate if the titration protocol is or is not maintained. Besides baseline factors such as age, sex, and duration of disease, the model will incorporate time-dependent factors including side effects. Missing data methods will address potential censoring of events among patients who fail to attend clinic visits.
  - b. We will run the same analysis using the biological threshold of sUA < 6.8 mg/dl at the end of phase 2.

- 3) To determine if there are gout flares in phase 3 in participants who achieve a sUA < 6.0 mg/dl by 48 weeks differ compared to those who do not, regardless of treatment assignment.

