  - a. We will carry out logistic regression analyses adjusting for covariates and use GEE model.
  - b. Baseline data include demographic characteristics (e.g. age, sex), disease history including CKD level, presence of tophi at baseline, height, weight, laboratory values, medications, other comorbidities, and quality-of-life measures.
  - c. Time-dependent variables include data obtained after baseline include sUA measures, titration levels, and side effects.
  - d. All data obtained before Phase 3 may be used as baseline factors for Phase 3 analyses.

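### The Protocol's adjusted models meant to confirm the primary result may use post-randomisation covariates and an odds-ratio link, so they do not estimate the difference the 8% bound refers to

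*Protocol*

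**What the plan says.** Protocol VIII sets the primary test: "The test of the primary hypothesis compares the treatments without adjustment for any covariates". A later sentence under Non-adherence allows the primary analysis a few covariates at most, but SAP 5.4 specifies the unadjusted difference.

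Protocol VIII then says that secondary analyses, including adjusted logistic models, "will confirm or not confirm the primary hypothesis by considering variations on the primary analysis". The mechanism is stated: "to carry out the non-inferiority test, we will estimate the difference between treatments by linking the odds ratio to the overall proportion". No formula, standard error or confidence limit follows.

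The same models carry over to stage 3 CKD under secondary objective 1: "we will carry out logistic regression analyses that adjust for covariates as described in the confirmatory analyses in objective 8".

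Objective 8 describes what may enter them. "Data obtained often after baseline include sUA values, titration levels, side effects, and gout flare counts". It then allows everything recorded before week 49: "All data obtained before Phase 3 may be used as baseline factors for Phase 3 analyses such as the primary hypothesis", and for the CKD 3 objective as well. SAP 5.5(8) repeats this: "All data obtained before Phase 3 may be used as baseline factors for Phase 3 analyses". SAP 5.3 also places baseline for the primary analysis at the start of Phase 3.

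On status, SAP 5.5 says: "All secondary analyses are descriptive exploratory analyses and will be done with and without covariate adjustment". The Protocol opens its Secondary Data Analysis section with the same statement.

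**The concern.** Two separate faults follow.

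1. **Post-randomisation covariates.** Study drug is titrated to sUA, so sUA, dose, side effects and flares in Phases 1 and 2 are partly consequences of the assigned drug. A model that holds them fixed removes or distorts part of the treatment effect. The 8% bound was chosen for the total difference in Phase 3 flare proportions. The size and sign of the distortion depend on the gap in target attainment and on common causes of sUA and flares, such as adherence.

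2. **The link.** A covariate-conditional odds ratio applied to one overall proportion is not the marginal risk difference, even when every covariate precedes randomisation. The answer also depends on what the overall proportion stands for.

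At stake is the supporting evidence. A model presented as confirming the primary decision could agree or disagree with it only because it measures something else.

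**Working it through.** **Inputs from the documents.** Bound 8 points, one-sided 5%, 450 per arm, febuxostat flare rate 20% (Protocol VIII). Cited final-month flare rates are 6% at sUA goal and 14% off goal. The Protocol expects roughly equal attainment of goal in the two arms, at 75–80%. **Assumed:** covariate strength (log-odds SD 0.5, 1.0, 1.5) and the attainment gaps.

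**Plan's own figure.** Power = Φ(0.08/√(2p(1−p)/450) − 1.645) gives 95.7%, 91.2% and 87.0% at flare rates of 15%, 20% and 25%. The Protocol states 96%, 91% and 87%, so the unadjusted design is reproduced.

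**Setting.** True risks are 28% (allopurinol) and 20% (febuxostat), a difference of exactly 8.0 points. A correct test should declare non-inferiority 5% of the time. The overall proportion is p = 0.24. Three readings of the link are possible:
- p as the febuxostat risk: expit(logit p + log OR) − p
- p as the average of the arms (pooled): solve for two risks with that odds ratio whose mean is p
- p as the allopurinol risk: p − expit(logit p − log OR)

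With linked difference L, pass rate = Φ((8 − L)/SE − 1.645), with SE by the delta method from SE(log OR) and p(1−p)/(2n).

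**No covariate effect.** OR = (0.28/0.72)/(0.20/0.80) = 1.556. The three readings give 8.9, 8.0 and 7.1 points. Only the pooled reading is exact, so the missing definition alone moves the answer by about 1 point either way.

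**Pre-randomisation covariate, pooled reading.** Intercepts are solved so that the marginal risks stay at 28% and 20%.

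| Log-odds SD | Conditional OR | Linked difference | Pass rate (nominal 5%) |
|---|---|---|---|
| 0.5 | 1.587 | 8.35 | 3.9% |
| 1.0 | 1.676 | 9.32 | 1.9% |
| 1.5 | 1.813 | 10.71 | 0.7% |

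Here the error is conservative. At a true difference of 0 and SD 1.0, simulation gave pass rates of about 87% for the link, 92% unadjusted and 94% for a standardised risk difference. At a true 8.0 points the standardised difference returned 8.0 points and passed 4.9–5.1%.

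**Adjusting for week-48 target status.** Flare ratio off versus at goal: 14/6 = 2.33, or compounded over six months (1 − 0.86⁶)/(1 − 0.94⁶) = 59.5/31.0 = 1.92. Only the ratio is used; levels are rescaled to a 20% febuxostat rate.

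For ratio 2.33 and 80% at goal on febuxostat, risk at goal = 0.20/(0.80 + 0.20 × 2.33) = 15.8% and off goal 36.8%. If allopurinol reaches 75%, the gap accounts for 0.05 × (36.8 − 15.8) ≈ 1.05 of the 8.0 points, leaving 6.95 within strata. Fitting the logistic model on treatment and target status, then linking (pooled):

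| At target, allopurinol / febuxostat | OR | Linked difference | Pass rate |
|---|---|---|---|
| 75% / 80% | 1.493–1.505 | 7.3–7.4 | about 8% |
| 80% / 80% | 1.571–1.584 | 8.2–8.3 | about 4–5% |
| 80% / 75% | 1.640–1.679 | 8.9–9.4 | about 2% |

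**The case against.** The strongest reply is that these models decide nothing. Both documents call secondary analyses exploratory and run them with and without adjustment, so an adjusted result would sit beside an unadjusted one. The permission is only that earlier data may be used. Objective 8 exists to describe covariate effects, including time-dependent ones. The SAP drops the odds-ratio link and the adjusted CKD 3 treatment model, sets no non-inferiority test for objective 8, and lists no adjusted model among its sensitivity analyses (5.4.1).

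Most of this stands, and it limits the point. The link fault belongs to the Protocol alone. What survives in the SAP is the permission itself, inside an exploratory objective. The label does not remove the problem in the Protocol, because the same section gives these models a confirming role and a non-inferiority test. That contradiction needs resolving, and no covariate list is fixed in advance.

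The size is also open to challenge. With equal attainment, which the Protocol expects, the pooled pass rate is close to nominal. SD 1.5 implies very strong baseline prediction, for which the documents give no source. Pass rates well above 8% arise only if the overall proportion is read as the allopurinol risk, which is not the natural reading.

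**Conclusion.** The point holds for the supporting models. As the Protocol describes them, they may adjust for consequences of treatment and they convert the odds ratio in a way that does not return the marginal risk difference. On the pooled reading the shift runs from under 1 point below the true 8.0 to nearly 3 above it. This rests on assumed covariate strengths and attainment gaps. It should be corrected, but it does not threaten the primary test.

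Three stronger readings are not supported:
- **That the primary decision is biased by this.** It is an unadjusted comparison and does not use these models.
- **That post-randomisation adjustment would usually confirm non-inferiority falsely.** If the whole 8-point deficit ran through sUA, an sUA-adjusted model would declare non-inferiority in 81–92% of simulated trials. That takes attainment gaps of 20 to 31 points and flare risks of 10–14% at goal against 40–50% off goal. The Protocol expects roughly equal attainment.
- **That the primary test is therefore secure at 5%.** The SAP's primary set is participants who tolerate treatment and remain on study when Phase 3 begins (3.3, 5.4). That is selection after randomisation, which the calculations above do not model and the fix does not address.

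**What to change.** - **Covariates.** In Protocol VIII (the adjusted-analysis paragraph, objective 1 and objective 8) and SAP 5.5(8), state that any adjusted model used to support the primary or CKD 3 non-inferiority result contains only covariates named in advance and measured at or before randomisation. The balancing factors plus age and sex would serve. First reconcile the fourth factor, which is prior ULT in Protocol VI but current allopurinol in SAP 5.2.
- **Estimator.** Replace the odds-ratio link with a standardised risk difference: average each participant's predicted risk under each arm, take the difference, and compare its one-sided 95% upper limit (delta method or bootstrap) with 8%.
- **Labels.** Call models containing post-randomisation variables descriptive, with no non-inferiority conclusion. Reconcile the confirming role in Protocol VIII with the exploratory status in both documents.

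The cost is a wording amendment, which Protocol XX says needs VA Central IRB approval before implementation, and standard SAS code. The suggested covariates are already collected. No new data are needed, and the post-randomisation models can still be run as description.
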